#### **10.2 Subject Accountability**

The number (and percent) of subjects who are enrolled, receive investigational product, and complete each study period will be summarized. The number (and percentage) of subjects who withdraw from treatment and from study will be summarized. The time of withdrawal and reason for withdrawal from IP or study will be listed. In addition, the number of subjects in each analysis set will be summarized.

#### **10.3 Important Protocol Deviations**

Important Protocol Deviations (IPDs) categories are defined by the study team before the first subject's visit and updated during the IPD reviews throughout the study prior to database lock. These definitions of IPD categories, sub-category codes and descriptions will be used during the course of the study. The final IPD list is used to produce the Summary of IPDs table and the List of Subjects with IPDs.

Eligibility deviations are defined in the protocol. Important inclusion/exclusion criteria deviations will be listed by subject.

#### **10.4 Demographic and Baseline Characteristics**

The following demographic and baseline characteristics will be summarized based on **FAS at Study 20140159 baseline and at baseline at first cinacalcet dose separately** using descriptive statistics:

Sex, age, dry weight, height, race group (white, black, other), ethnicity, dialysis status, Tanner stage, baseline iPTH, corrected total serum calcium, ionized calcium, serum phosphorous, Ca x P, and selected concomitant medication.

#### **10.5 Analysis of Primary Endpoint**

The primary endpoint is incidence of treatment emergent adverse events of interest as defined in **Section 6.4**. The analysis will be based on Safety Analysis Set. Subject incidence of EOIs will be summarized by EOI category and **preferred term for data in Study 20140159 only for both the interim and final analyses. The 95% confidence intervals (CI) of the overall subject incidence rates will be reported.**

**The secondary analysis of the primary endpoint is follow-up time adjusted incidence of EOIs for combined data from parent studies and data from the 20140159 study for the final analysis.**

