**5. Hypotheses and/or Estimations**

There is no formal statistical testing for this study. The proportions of subjects with treatment emergent adverse events of interest will be estimated.

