**Time on study**

If the subject has ended study, time on study (in days) is defined as: time on study = end of study date – study Day 1 +1.

Otherwise, time on study (in days) = data cutoff day – study Day 1 +1, which is applicable for interim analysis only.

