**End of study Date (for interim analysis only)**

For subjects who completed the study or early terminated from the study as of the data cut-off date, the end of study date is the date on the end of study form. For subjects who are ongoing as of cutoff date, leave the end of study date as missing.

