### 7.2 Safety Analysis Set

The Safety Analysis Set will be used for primary and safety endpoints. It includes all subjects who were enrolled in Study 20140159 and received at least one dose of investigational product. **Subjects will be analyzed according to the treatment received in the parent studies and overall.**

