### 8. Interim Analysis and Early Stopping Guidelines

An interim analysis will be performed to support the sNDA for the pediatric indication. The scope of this interim analysis will be specified in **section 10** of this SAP. Additional interim analyses may be performed if necessary to support regulatory inquiries and the SAP may be amended to reflect the additional analyses. There are no plans to change the conduct of the study based on the interim analysis results.

There is no formal statistical testing. The analysis for all endpoints will be descriptive in nature.

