**The laboratory data collected more than 7 days after the last dose of IP will be excluded for the efficacy analyses.**

**For the interim analysis supporting pediatric sNDA, only data from the 20140159 study before interim data cutoff date will be analyzed according to the actual treatment received from the parent study and overall.**

**For the final analysis, final efficacy and safety data from Study 20140159 will be analyzed. In addition, cumulative data combining the parent studies (20130356 and 20110100) and Study 20140159 will also be summarized.**

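### At the sNDA interim the primary safety endpoint is planned only as a crude percentage of dosed children; if any are still ongoing at the cutoff, it understates event-of-interest risk over the planned 28+4 weeks

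*SAP*

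**What the plan says.** **Measure.** SAP 5 sets the aim: "The proportions of subjects with treatment emergent adverse events of interest will be estimated". SAP 10.5 reports subject incidence by EOI category and "preferred term for data in Study 20140159 only for both the interim and final analyses", with a 95% CI whose method is not named.

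**Denominator.** SAP 7.2 defines the Safety Analysis Set: "It includes all subjects who were enrolled in Study 20140159 and received at least one dose of investigational product". It sets no minimum exposure or follow-up.

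**Interim.** SAP 8 gives its purpose: "An interim analysis will be performed to support the sNDA for the pediatric indication". SAP 10.1 fixes the data: "For the interim analysis supporting pediatric sNDA, only data from the 20140159 study before interim data cutoff date will be analyzed". Neither document gives the cutoff date. Protocol 10.3.1 likewise limits the first interim to extension-study data.

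**Ongoing children.** SAP 6.2 (End of study Date, interim) says: "For subjects who are ongoing as of cutoff date, leave the end of study date as missing". SAP 6.1 defines a time on study that runs to the cutoff for those who have not ended the study, "which is applicable for interim analysis only". No EOI analysis in SAP Section 10 uses that variable.

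**Follow-up adjustment.** SAP 10.5 plans it once: "The secondary analysis of the primary endpoint is follow-up time adjusted incidence of EOIs for combined data from parent studies" and the extension, at the final analysis. Its time variable (SAP 6.1, Time of follow-up) is designated for the final analysis and is computed from the end of study date, which ongoing children lack at the interim.

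**The concern.** Cumulative incidence cannot fall with time. A child observed for 6 of 32 weeks has had at most the 32-week risk, but counts as one full unit in the denominator. A crude percentage over a mix of finished and ongoing children therefore averages risks over different periods, and that average sits at or below the risk over the full planned period.

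The plan recognises that follow-up varies, because it adjusts for it in the combined final analysis. It makes no such adjustment at the interim, where staggered entry can make follow-up most uneven and where the result goes into a filing. The primary objective is long-term safety (SAP 2.1), so a reader will naturally take the percentage as the risk over the study period. If children are ongoing, the number instead depends partly on when they enrolled, and its 95% CI does not reflect this.

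**Working it through.** **The plan's own figure.** The only planning number is the sample size in SAP 3.2: 48 + 30 = 78, which reproduces. No expected EOI rate or precision is stated.

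**Inputs from the documents.** Full follow-up is 28 + 4 = 32 weeks (Protocol 3.5.1). The denominator is all dosed children (SAP 7.2). The maximum n is 78.

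**Assumptions (not in the documents).** The true 32-week risk is R. A fraction g of dosed children is ongoing at the cutoff, with follow-up uniform over 0-32 weeks, and the rest have complete follow-up. The hazard is either constant (Weibull shape k = 1) or front-loaded (k = 0.5).

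**Formula.** With λ = −ln(1−R), risk by week t is F(t) = 1 − exp[−λ(t/32)^k]. The expected crude percentage is (1−g)·R + g·M, where M is the mean of F(t) over 0-32 weeks.

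**Worked case, R = 30%.** λ = −ln 0.7 = 0.3567.

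- Constant hazard: M = 1 − 0.30/0.3567 = 15.9%. At g = 50%: 0.5 × 30 + 0.5 × 15.9 = 22.9%.
- Front-loaded: M = 1 − 2[1 − 0.7 × 1.3567]/0.3567² = 20.9%. At g = 50%: 0.5 × 30 + 0.5 × 20.9 = 25.4%.

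| Ongoing at cutoff | Constant hazard | Relative to 30% | Front-loaded | Relative to 30% |
|---|---|---|---|---|
| 0% | 30.0% | 0 | 30.0% | 0 |
| 25% | 26.5% | −12% | 27.7% | −8% |
| 50% | 22.9% | −24% | 25.4% | −15% |
| 75% | 19.4% | −35% | 23.2% | −23% |

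**Other risks.** For R from 5% to 50%, the ratio of crude to true at 25/50/75% ongoing is 0.88-0.89, 0.75-0.78 and 0.63-0.67 (constant), or 0.92-0.93, 0.84-0.86 and 0.75-0.79 (front-loaded).

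**Confidence interval.** This was simulated with n = 78, using the exact binomial interval as an assumption because the SAP names none. Coverage of the 32-week risk at 25/50/75% ongoing:

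- R = 30%, constant hazard: about 90%, 74% and 46%.
- R = 30%, front-loaded: about 94%, 87% and 75%.
- R = 10%, constant hazard: about 96%, 94% and 88%. For rare events the wide interval hides most of the shift.

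**Does the remedy recover the target?** In the same simulations at R = 30%, Kaplan-Meier at week 32 averaged 29.7% to 30.2% under both hazards. A single person-time rate converted to 32-week risk gave about 30% under constant hazard, but 32.8%, 34.5% and 36.4% under the front-loaded one.

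**Time point.** Under constant hazard, the week-28 risk matching a 30% week-32 risk is 1 − 0.7^(28/32) = 26.8%. A week-28 estimate is therefore a different quantity.

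**The case against.** **The crude figure is a correct count.** SAP 5 promises proportions in a descriptive study, and SAP 10.5 sets no 32-week target. This stands: the percentage correctly describes events seen by the cutoff. It is low only as a measure of risk over the full planned period, which is how a long-term safety figure is likely to be read.

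**The shortfall may be nil.** A reader might infer that the filing figure is certainly biased low, or that it includes many children only weeks into treatment. The documents support neither. The rules for ongoing children are conditional definitions, and no cutoff date, accrual pattern or minimum follow-up is given. If every dosed child has finished, the staggered-entry effect is zero.

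**Incomplete follow-up would be visible.** SAP 10.2 tabulates completion and withdrawal, and SAP 10.7.5 summarises days on treatment. These would alert a careful reader, but neither table is linked to EOI incidence or adjusts it.

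**The final analysis.** A reader might extend the point to children who leave early. That is weak. Transplant and parathyroidectomy are reasons for removal from treatment (Protocol 8.2.1) but not from study (8.2.2), and adverse events are collected for 30 days after the last dose (7.3.10). Allowing for those 30 days, with an assumed 15-30% leaving evenly over weeks 1-28 and a 30% risk, the effect is about −6% to −11% (constant) or −3% to −7% (front-loaded). It is at most a minor note.

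**Conclusion.** The gap is real but conditional. At the analysis meant to support the sNDA, the only planned primary-endpoint estimate is a crude percentage of all dosed children. The SAP provides for ongoing children there and plans no adjustment for their shorter follow-up. If any are ongoing, the figure tends to understate 28+4-week EOI risk. The direction follows from cumulative incidence being non-decreasing.

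The size cannot be read from the documents. With 25% to 75% ongoing it is roughly 8% to 35% of a true 30% risk across the two hazard shapes tried. The event rate, ongoing fraction, uniform follow-up and hazard shapes are all assumptions. The missing analysis is certain; the amount of understatement is not. Because the remedy is cheap and uses dates already defined, the change should be made.

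**What to change.** In SAP 10.5, for 20140159-only data at the interim, keep the crude percentage and place beside it:

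- **(a)** the number of children ongoing at the cutoff and the median follow-up;
- **(b)** the Kaplan-Meier cumulative incidence of first event for each EOI, with numbers at risk. Time runs from Study Day 1 to first event, censored at the earlier of the end of adverse event follow-up and the data cutoff. Report it at week 32 to match full follow-up, or at week 28 if labelled as on-treatment risk;
- **(c)** optionally, the first-event rate per 100 subject-years with an exact Poisson 95% CI, not projected to 32 weeks because events may cluster early.

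**Cost.** SAP wording and one extra table, with no change to conduct or data collection. Study Day 1 and cutoff-based time on study are already defined in SAP 6.1 and 6.2. Some reported safety figures will be higher. Kaplan-Meier assumes non-informative censoring, which is easier to defend for administrative censoring at the cutoff than for children who leave early, so the number censored for each reason should be shown. Late estimates will be imprecise where few children have reached week 32.

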## 10.6 Efficacy Analyses

### 10.6.1 Analyses of Secondary Endpoints

Analyses of secondary endpoints will be based on **Efficacy Analysis Set or 20130356 SOC Set per endpoint definitions unless otherwise specified.**

#### Study20140159only

Proportion of subjects achieving the secondary endpoints of  $\geq 30\%$  reduction in iPTH from study baseline to mean value during weeks 11 and 15 will be reported with 95% CI based on 20130356 SOC Set. Subjects who have no iPTH values during weeks 11 or 15 will be considered non-responders.

Proportion of subjects achieving the secondary endpoints of  $\geq 30\%$  reduction in iPTH from study baseline to mean value during weeks 23 and 28 will be reported with 95% CI based on 20130356 SOC Set. For subjects who do not have a iPTH value during weeks 23 and 28, the mean of the last two available post-baseline values in the dose-titration phase will be used. If only one post-baseline value is available, this single value will be used. If no post-baseline value is available, the subject is considered a non-responder.

Summary statistics will be provided for percent change from study baseline to mean iPTH during weeks 23 and 28 based on 20130356 SOC Set, and change in corrected total calcium and change in serum phosphorus from study baseline to mean value during weeks 23 and 28 based on efficacy analysis set by treatment group in the parent studies. For subjects who are missing the efficacy measurement during weeks 23 to 28, the mean of the last two available post-baseline values in the dose titration phase will be used. If only one post-baseline value is available, this single value will be used. If no post-baseline value is available, the subject will be excluded from the analysis.

Proportion of subjects who achieve a mean iPTH value  $\leq 300$  pg/mL during weeks 23 and 28 will be provided based on efficacy analysis set by the treatment group in parent study with 95% CI. For subjects who do not have an iPTH value during weeks 23 and 28, the mean of the last two available post-baseline values in the dose-titration phase will be used. If only one post-baseline value is available, this single value will be used. If no post-baseline value is available, the subject is considered a non-responder.

**Summary statistics will be provided for serum cCa and phosphorus values at study baseline, week 11, and week 28 for all efficacy analysis set subjects.**

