#### **Secondary Endpoints:**

##### **20140159studyonly(forinterimandfinalanalyses)**

Achievement of  $\geq$ 30% reduction from baseline to mean iPTH during weeks 11 and 15 (SOC arm of Study 20130356 only)

Achievement of  $\geq$ 30% reduction from baseline to mean iPTH during weeks 23 and 28 (SOC arm of Study 20130356 only)

Percent change from baseline to mean iPTH during weeks 23 and 28 (SOC arm of Study 20130356 only)

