**End of treatment**

For subject who completed treatment as of cutoff date, the end of treatment is defined as the date of the last dose of IP. If subject is ongoing as of cutoff date, leave as missing.

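### At the sNDA interim, SAP 10.6.1 has no rule for visits not yet due at the cut-off: they count as week 11/15 non-response or are filled with earlier values for weeks 23/28

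*SAP*

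**What the plan says.** SAP section 4 assigns the Study 20140159-only secondary endpoints to both the interim and the final analysis. SAP section 8 states: "An interim analysis will be performed to support the sNDA for the pediatric indication", and refers to section 10 for its scope. SAP 10.1 adds: "For the interim analysis supporting pediatric sNDA, only data from the 20140159 study before interim data cutoff date will be analyzed".

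The SAP expects some subjects to be still on study at that point:
- Time on study has a version that runs to the cut-off, "which is applicable for interim analysis only" (6.1).
- For end of treatment: "If subject is ongoing as of cutoff date, leave as missing" (6.2).
- For the interim end-of-study date: "For subjects who are ongoing as of cutoff date, leave the end of study date as missing" (6.2).

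The Efficacy Analysis Set (7.3) and the Study 20130356 SOC Set (7.4) each require one dose and one assessment after Study Day 1. Neither sets a minimum follow-up.

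SAP 10.6.1 then gives one set of missing-value rules:
- Week 11/15 responder endpoint (SOC Set): "Subjects who have no iPTH values during weeks 11 or 15 will be considered non-responders".
- Week 23/28 endpoints with no value in that period: use the average of the two most recent titration-phase results, or the single one if only one exists.
- Week 23/28 iPTH proportions with nothing after baseline: "If no post-baseline value is available, the subject is considered a non-responder". For the continuous week 23/28 endpoints such a subject is left out.

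**The concern.** These rules suit a final analysis, where an absent value means a missed visit or a discontinuation. At an interim there is a third reason: the visit has not happened yet. The SAP adapts its date definitions for ongoing subjects but not its endpoint rules. A recently enrolled subject can therefore be scored as a failure, or be given a week 23/28 result taken from the first weeks of treatment.

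The interim responder proportions and week 23/28 changes would then partly measure how recently subjects enrolled. They are secondary and descriptive, but they are produced, the proportions with 95% confidence intervals, to support a regulatory submission.

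**Working it through.** **Inputs**
- SAP 3.2: 48 + 30 = 78, which reproduces the stated planned size.
- Protocol 2.5.1: 1:1 allocation of about 48, so the SOC Set is at most about 48/2 = 24.
- SAP 6.2 iPTH windows: week 3, days 2-36; week 11, days 65-92; week 23, days 149-176. Target day = 7 x week + 1. Calcium and phosphorus add week 1, days 2-14.
- Protocol 6.2.3.1.1.1: dose increases only at weeks 4, 8, 12, 16, 20 and 24, taken as days 29, 57, 85, 113, 141 and 169.
- SAP 6.1 gives only the end of the titration phase (week 24); its start is taken as Study Day 1.
- Response rates and numbers not yet due are assumptions. Intervals are exact (Clopper-Pearson), because the SAP names no method.

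**(a) Weeks 11/15.** Suppose k of 24 SOC subjects have not reached week 11, and due and not-yet-due subjects share the same true response rate p. Then reported rate = p x (24 - k)/24 = p x (1 - f), with f = k/24.

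| True p | k = 0 | 2 | 4 | 6 | 8 |
|---|---|---|---|---|---|
| 40% | 40 | 37 | 33 | 30 | 27 |
| 60% | 60 | 55 | 50 | 45 | 40 |
| 80% | 80 | 73 | 67 | 60 | 53 |

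Example with k = 6 and 11 responders among the 18 due: as written, 11/24 = 45.8% (25.6 to 67.2); among those due, 11/18 = 61.1% (35.7 to 82.7). The shift is always downward.

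**(b) Weeks 23/28.** With samples on target days, the value substituted depends on the study day at cut-off. The last column counts permitted dose increases before each sample. It applies to SOC subjects and to those restarting after a gap of more than 14 days.

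| Day at cut-off | Value used | Increases possible before it |
|---|---|---|
| 8-21 | Ca, P: week 1 only | 0 |
| 22-49 | iPTH: week 3 only; Ca, P: weeks 1 + 3 | 0 |
| 50-77 | weeks 3 + 7 | 0, 1 |
| 78-105 | weeks 7 + 11 | 1, 2 |
| 106-133 | weeks 11 + 15 | 2, 3 |
| 134-161 | weeks 15 + 19 | 3, 4 |

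On-schedule week 23 and week 28 samples (days 162 and 197) follow 5 and 6. The direction of the error depends on how values move over time and is not fixed.

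**(c) No iPTH yet.** A week 1 ionized calcium is enough to enter either set, but the first scheduled post-baseline iPTH is at week 3. Subjects cut off at about days 8 to 21 are therefore non-responders for both week 23/28 iPTH proportions.

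**The case against.** **The size is not known.** This stands. The definitions for ongoing subjects show that such subjects are allowed for, not that any will be short of day 65 or day 149 at cut-off. A reader might infer that the interim results are certain to be biased; the documents do not support that.

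**Early values are not necessarily pre-titration values.** This also stands. A reader might infer that a substituted week 3 iPTH always precedes any dose increase. That holds on the scheduled day, but the window runs to day 36, past the week 4 visit on day 29. A reader might also apply the count of increases to everyone. By planned sizes, up to 78 - 24 = 54 subjects come from outside the SOC arm, and Protocol 6.2.3 lets those with a gap of 14 days or less continue their parent-study dose. Their early values can follow months of earlier titration. This matters for the calcium, phosphorus and iPTH <= 300 pg/mL endpoints, which use the whole Efficacy set.

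**Other outputs reveal the immaturity.** Partly so. Accountability (10.2), by-visit laboratory summaries (10.7.2) and exposure (10.7.5) would show incomplete follow-up, but they do not correct the proportions or the substituted summaries. The interim per-protocol analysis (10.6.2) needs an in-window value, but it also removes protocol deviators and non-compliers, so it does not isolate the effect. The completer, inverse-probability-weighted and nearest-two analyses are for the final analysis only.

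**Non-responder scoring is conservative.** That argument fits missed visits and dropouts. A visit not yet due says nothing about failure, and the week 23/28 substitution is not reliably conservative.

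**A separate interim SAP could deal with it.** Protocol 10.3.1 mentions one after its sentence on the later interims. For the sNDA interim, SAP section 8 relies on section 10 of this SAP.

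**Conclusion.** The gap is real and conditional. As written, SAP 10.6.1 scores a week 11/15 visit not yet due as a failure, and it fills weeks 23/28 with earlier values. If a share f of the SOC Set has not reached week 11, the week 11/15 rate is multiplied by (1 - f); with 6 of 24 not yet due, an assumed true 60% reads 45%. The week 23/28 error has no fixed sign and is hardest to interpret in SOC subjects and in those restarting after more than 14 days.

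The documents give no cut-off date or accrual, so every size here rests on assumed values; the effect is zero if all subjects have passed the windows. The affected endpoints are secondary and descriptive, and SAP section 8 rules out changes to study conduct on interim results. The week 11 and week 28 calcium and phosphorus summaries, which carry no imputation rule, are not affected, nor is the final analysis.

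**What to change.** Add to SAP 10.6.1, for the interim only:
- The week 11/15 endpoint includes subjects with (cut-off date - Study Day 1 + 1) >= 92.
- The imputed week 23/28 endpoints include subjects for whom this is >= 176.
- Membership is decided by Study Day 1 date alone, whether or not investigational product was stopped. Keeping early discontinuations while dropping ongoing subjects of the same vintage would tilt the result.
- Within each group, the existing rules for missed visits and discontinuations stay.
- Each table shows the number not yet due. The proportion as now defined may stay as a secondary display.

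Days 92 and 176 are the closing days of the week 11 and week 23 windows. Some included subjects will contribute only a week 11 or only a week 23 value, which the present rules already accept.

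The wording is cheap, and nothing changes if everyone has passed the windows. The real cost is precision. At 50% response the exact interval is 26 to 74% with 18 subjects, against 29 to 71% with 24. If ongoing subjects are spread evenly over days 1 to 225 (an assumption), the rules exclude 91/225 = 40% of them at day 92 and 175/225 = 78% at day 176. Of these, 14/225 = 6% in each case are excluded despite an on-schedule in-window value (days 78-91 and 162-175). The interim week 23/28 results may therefore rest on few subjects, and the table should make that visible.

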# 3. EXPERIMENTAL PLAN

#### 3.1 Study Design

This is a phase 3, 32-week, multicenter, single-arm, extension study designed to characterize the long-term safety and tolerability of cinacalcet in pediatric subjects. Subjects will remain on cinacalcet treatment for 28 weeks after enrollment or until the time of renal transplant or parathyroidectomy, whichever occurs first. The treatment period is followed by a 4-week safety follow-up period.

The overall study design is described by a **Study Design and Treatment Schema** at the end of the protocol synopsis section.

The study endpoints are defined in Section 10.1.1.

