**End of dose titration phase**

The end of dose titration phase is Week 24 of Study 20140159.

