**Combined 20130356, 20110100 & 20140159 studies**

**Proportion of subjects achieving the secondary endpoints of  $\geq 30\%$  reduction in iPTH from day 1 of cinacalcet treatment to mean value during weeks 11 and 15 will be reported with 95% CI for all efficacy analysis set subjects. Subjects who have no weeks 11 or 15 iPTH values will be considered non-responders.**

**Proportion of subjects achieving the secondary endpoints of  $\geq 30\%$  reduction in iPTH from day 1 of cinacalcet treatment to mean value during weeks 23 and 28 will be reported with 95% CI for all efficacy analysis set subjects. For subjects who do not have an iPTH value during weeks 23 and 28, the mean of the last two available post-baseline values collected at protocol-specified visits in the dose titration phase will be used. If only one post-baseline value is available, this single value will be used. If no post-baseline value is available, the subject is considered a non-responder.**

**Summary statistics will be provided for percent change in iPTH, change in serum cCa and change in serum phosphorus over time from day 1 of cinacalcet treatment for all efficacy analysis set subjects.**

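### At weeks 23/28, subjects without iPTH are scored on carried-forward values, whereas at weeks 11/15 they count as failures, and no planned analysis shows the later responder rates under the stricter rule

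*SAP*

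**What the plan says.** SAP 10.6.1 (Study 20140159 only) has two rules for the ≥30% reduction endpoint, analysed in the Study 20130356 SOC Set.

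- Weeks 11/15: "Subjects who have no iPTH values during weeks 11 or 15 will be considered non-responders".
- Weeks 23/28: "the mean of the last two available post-baseline values in the dose-titration phase will be used". If only one post-baseline value exists, that value is used. Failure by rule is the last resort: "If no post-baseline value is available, the subject is considered a non-responder".

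The endpoint of mean iPTH ≤300 pg/mL at weeks 23/28, in the Efficacy Analysis Set, has the same carry-forward.

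The combined-study analyses repeat the pair. At weeks 11/15, "Subjects who have no weeks 11 or 15 iPTH values will be considered non-responders"; at weeks 23/28, "the mean of the last two available post-baseline values collected at protocol-specified visits in the dose titration phase will be used".

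Two further statements fix what can be carried. SAP 10.1: "The laboratory data collected more than 7 days after the last dose of IP will be excluded for the efficacy analyses". SAP 6.1: "The end of dose titration phase is Week 24 of Study 20140159".

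SAP 10.6.2 lists IPW, completer and per-protocol sensitivity analyses for the weeks 23/28 responder endpoints. For the 20140159-only endpoints, per protocol is planned at interim and final, and the other two at final only. The combined endpoints are final-only throughout.

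**The concern.** The two periods treat missing iPTH in opposite ways, and the SAP gives no reason for the change. A subject who leaves treatment early can count as a long-term responder on values obtained before leaving. Off-drug results do not correct this: beyond 7 days after the last dose they are excluded, the later window becomes empty, and carry-forward applies.

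Both proportions are reported with 95% confidence intervals in a study meant to describe long-term effect, so readers will set them side by side. A rate that appears to hold or rise between the periods could come partly from the change of rule. At the interim, which supports the pediatric sNDA, the only planned check leaves out anyone without a value in the window.

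**Working it through.** **Inputs.** SAP 3.2 gives 48 + 30 = 78 subjects, which reproduces. Protocol 2.5.1 randomises about 48 in a 1:1 ratio, so the SOC set is at most 48/2 = 24. It may be smaller, because former SOC subjects must have iPTH ≥300 pg/mL and corrected calcium ≥8.8 mg/dL to enter. The documents give no dropout rate and no response rate. The values of d, p and r below are assumptions.

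**Formula.** Let d be the share with no iPTH in either the week 23 or the week 28 window but with an earlier value, p the response among those observed, and r the share of carried subjects whose carried mean meets the criterion.

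- Rate under the weeks 11/15 rule (non-responder imputation): (1 − d)p
- Rate under the SAP's weeks 23/28 rule: (1 − d)p + d·r
- Excess: d·r, which is never negative and is zero when r = 0

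**Range.**

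| d | r = 25% | r = 50% | r = 75% |
|---|---|---|---|
| 10% | 2.5 points | 5 points | 7.5 points |
| 20% | 5 points | 10 points | 15 points |
| 40% | 10 points | 20 points | 30 points |

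**In counts (p about 50%, exact 95% CI).** Take a SOC set of 24 with 5 subjects carried and 10 responders among the 19 observed.

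- Non-responder imputation: 10/24 = 41.7% (22.1 to 63.4)
- SAP rule, no carried subject responding: 10/24 = 41.7%
- SAP rule, 2 of 5 responding: 12/24 = 50.0% (29.1 to 70.9)
- SAP rule, all 5 responding: 15/24 = 62.5% (40.6 to 81.2)

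Each carried responder adds 1/24 = 4.2 points. For iPTH ≤300 pg/mL in a full set of 78 with 16 carried and 31 observed responders, the rate runs from 31/78 = 39.7% to 47/78 = 60.3%.

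**Who can change from failure to success.** In the iPTH windows of SAP 6.2, week 3 is days 2–36, week 7 is days 37–64, and weeks 11 and 15 together are days 65–120. A subject with only week 3 and week 7 values is a failure at weeks 11/15. If the mean of those two values is at least 30% below baseline, the same subject is a success at weeks 23/28, with no new data. A subject who leaves after a week 11 value is scored on that value at weeks 11/15. That subject cannot change status through the missing-data rule at weeks 11/15, but an early response is still carried into the later rate. The part of d·r that can create a rise through the rule change is therefore limited to subjects with nothing in days 65–120.

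**What the planned analyses do with these subjects at weeks 23/28.**

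| Analysis | Treatment of subjects with no value | Timing, 20140159-only |
|---|---|---|
| IPW | Represented by reweighted observed subjects | Final |
| Completer | Dropped | Final |
| Per protocol | Dropped | Interim and final |

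None counts them as non-responders. Weeks 11/15 does have the reverse check: nearest-2 imputation tests the non-responder rule there.

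**Interim.** SAP 6.1 and 6.2 provide for subjects still ongoing at the data cutoff. The carry-forward wording does not separate them from leavers, so an ongoing subject with only early values would also enter the weeks 23/28 rate.

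**The case against.** A reader might infer that the weeks 23/28 rates *are* inflated. The documents do not show that. The algebra places the SAP rate at or above non-responder imputation, but that imputation is itself an assumption, and the excess may be zero. Week 3 values precede any dose increase, and week 7 values follow at most one. Measured against what leavers would have shown had they stayed on drug, carried values could understate response.

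A reader might also infer that subjects stopped for over-suppression or hypocalcaemia, with a low last iPTH, become the false responders. Protocol 6.2.3.1.1.1 and Table 1 handle those findings by withholding and later restarting, with iPTH still scheduled at weeks 23 and 28. The design names other events that end treatment: "until the time of renal transplant or parathyroidectomy, whichever occurs first". Removal for an adverse event is possible, but nothing in the documents says what the last iPTH would be.

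These further limits stand:

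- The ≤300 pg/mL endpoint has no weeks 11/15 counterpart, so for it the gap is the missing check and not a conflict of rules.
- The combined analysis is less exposed. Subjects treated for about 20 to 24 weeks in a parent study reach cinacalcet weeks 23/28 around or soon after entry.
- Missing data are not ignored. Three sensitivity analyses are planned, and withdrawal times and reasons are listed. At the final analysis, completer responders divided by the full set give the non-responder rate. However, that figure is not prespecified, and no completer analysis exists at the interim.
- Everything is descriptive, no formal comparison of the two periods is planned, and no error rate is affected.

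**Conclusion.** The point holds in a limited form. SAP 10.6.1 applies opposite missing-data rules to the ≥30% endpoint, the carried values are on-drug or within 7 days of the last dose, and no planned analysis scores leavers as failures at weeks 23/28. The later rates can exceed the rate under the weeks 11/15 rule by d × r: 2.5 to 30 points for assumed d of 10–40% and r of 25–75%, and zero if no carried subject meets the criterion. The firm figure is 4.2 points per carried responder in a SOC set of 24, which is its ceiling; in a smaller set each one weighs more. The whole of d × r should not be read as an artificial rise between periods, because only subjects with no value in days 65–120 can move from failure to success by rule. This is a cheap improvement to a descriptive secondary analysis and does not show that the planned rates are wrong. It assumes that carry-forward applies only when both the week 23 and week 28 windows are empty.

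**What to change.** In SAP 10.6.2, add a non-responder imputation sensitivity analysis for the weeks 23/28 responder endpoints and present it beside the carry-forward result:

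- the 20140159-only endpoints (≥30% reduction and iPTH ≤300 pg/mL) at interim and final;
- the combined ≥30% endpoint at final only.

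Report for each the number of subjects carried forward, with reasons.

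At the interim, limit the analysis to subjects who reached the weeks 23/28 window or who ended treatment or study before it. Show ongoing subjects separately, so that they are scored neither as failures nor on early values.

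The cost is a short SAP addition and one extra table per endpoint. The added rate may be less favourable than the carry-forward rate.
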